5 PROCEDURES

5.1 Study procedures. Using lay language, provide a complete description of the study procedures, including the sequence, intervention or manipulation (if any), time required, and setting/location. If it is available and you think it would be helpful to the IRB: Upload a study flow sheet or table to the **Supporting Documents** SmartForm in **Zipline**.

For studies comparing standards of care: It is important to accurately identify the research procedures. See UW IRB [POLICY: Risks of Harm from Standard Care](#) and the draft guidance from the federal Office of Human Research Protections, ["Guidance on Disclosing Reasonably Foreseeable Risks in Research Evaluating Standards of Care"](#), October 20, 2014.

Study Interventions

In this study, we are using a Stepped wedge design that randomizes at the site level. That means that all clients will receive whichever intervention their site is providing at the time they enroll. This will be Treatment as Usual (TAU) until the Stepped wedge design randomization selects that site to implement PARS at which point all clients will receive PARS till the end of the study. This will be true for all clients and counselors whether or not they choose to participate in the study. Thus, the study is restricting the choice of interventions for study participants and non-participants.

This is described in the consent form for participants. However, because of the study design, non-subjects will also experience randomization and exposure to the intervention. We request a waiver of consent for this.

Clarification of IOP Treatment in which both study interventions are embedded

Intensive Outpatient Program (IOP) guidelines in Washington State are based on State requirements. Within these guidelines, agencies typically offer IOP consisting of three-hour groups, three times a week, over eight weeks, for a total of 24 groups (72 hours total). Some programs meet less often for a longer time window up to 12 weeks. The 24-36 session series runs and then starts over continuously. Clients can enter the IOP at any time in the 24 session series and stay until they have attended all 24-36 sessions. Thus, within 24-36 sessions, all IOP clients will have completed (or dropped) from the program and a new group of IOP participants will be in the program. In our Stepped wedge design, each step is 4 months, which means that when we return to the site at each step, we will be recruiting from a different pool of clients.

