each site will be consented and complete a baseline assessment. (Standard IOP groups in Washington have 12-15 clients registered and, given 98% of those approached in our pilot study consented, it is expected this will be sufficient.) Participants will be assessed post-intervention and followed up at 1, 3, and 6 months with brief online (or phone, if online or text is not feasible for the participant). Study staff will evaluate counselors at each site to assure fidelity to PARS once trained; supervising as needed throughout the study.

C3. Design.

Treatment Conditions

Control: Treatment as Usual (TAU)

Intensive Outpatient Program (IOP) guidelines in Washington State are based on State requirements.^{33,34} Within these guidelines, agencies typically offer IOP consisting of three-hour groups, three times a week, over eight weeks, for a total of 24 groups (meeting both State and deferred prosecution requirements). Some programs meet less often for a longer time window up to 12 weeks. Although at least one monthly individual counseling session is required, the primary modality is a group format. IOP programs are required to provide education on specific topics, e.g., alcohol and drug education, relapse prevention, risks of drug or alcohol use during pregnancy, blood borne pathogens (including HIV/AIDS and Hepatitis), emotional, physical, and sexual abuse, and nicotine addiction. However, within a 24-group curriculum, IOP programs have wide latitude in determining group content since the required topics typically represent less than 50% of the 24 groups. Therefore the content in IOP programs across our sites is expected to be variable while the structure of session hours and attendance will be consistent. However, no IOP programs include suicide prevention.

At the beginning of the study, each site will select a particular group session in their 24-session schedule to replace with PARS. *They will move that session to the place where PARS will be at the start of the study. To minimize variability between sites, the session to be replaced will be one regarding grief, depression, or coping with negative emotions. While sites vary on what exactly they teach in this general content, all have something they are willing to replace in this non-required section of their IOP, reducing site variability for this study.*

Intervention: TAU + Preventing Addiction Related Suicide (PARS)

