This study will use a stepped wedge design as shown in Figure 1. This design is recommended for studies in which it is beneficial to randomize at the site rather than individual level.³⁵⁻³⁷ Such is the case in this study, as randomization at the individual level would not be feasible with our community partners, who are enrolling clients and placing them in groups based on many complex reasons including client schedules, IOP group schedules and openings, and a myriad of agency guidelines and regulations. Such a study would require conducting PARS and usual care in a research clinic setting—which is the opposite of our goal. PARS was developed in community settings and its effectiveness in those settings is key. Once it was determined that randomization would be at the site level, both clustered randomized and stepped wedge designs were considered.^{35,37-44} While both have benefits, the stepped wedge has the advantage of measuring dose-response (delay) effects. Furthermore, its primary disadvantage (that more assessment points were required)^{35,40,42} was not determined to be a problem for the research team or community partners, as participants would complete the same assessments regardless of stepped wedge or cluster randomization.

In the proposed study, there will be six steps. Steps will be 6 months each to assure sufficient time for all data collection to occur given that some IOP programs are as long as 12 weeks and sites will vary as to which session PARS replaces in their IOP curricula. In each of the six steps of the study, baseline assessments will be conducted the week before that selected session at that site. For instance, Site A might replace session 8 with PARS but Site B might replace session 14, so baseline assessments will be conducted in week 7 at Site A and week 13 at Site B. (Data collection methods for baseline assessments described in Procedures below.) This will assure that the follow-up assessments reflect the period after PARS is administered while allowing the natural variation in IOP curriculum that is inevitable with 15 community partner sites.

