As per the stepped wedge design (see Figure 1), the 15 sites will be randomly assigned to 5 groups of three sites each. At Step 1, all sites will be in the TAU condition. The 5 groups will then be randomly assigned to begin PARS at one of the subsequent 5 steps (i.e., Step 2-6). Once beginning PARS, they will continue to administer PARS through the end of Step 6. Thus, three sites per step will begin administering PARS—until by Step 6, all sites are administering PARS.

[name], stepped wedge design expert (as can be seen in his Biosketch), has reviewed and approved our design (as noted in his Letter of Support) and is available for consultation as needed.

C4. Participants.

Setting. Participants (N=900) will be recruited from 15 community treatment sites in Washington State from the four treatment agencies that are our community partners in this study. As can be seen from their Letters of Support, our community partners are enthusiastic about PARS and see both the program and the study design

as feasible and acceptable. Sites represent urban and rural areas in Washington as well as representing sites primarily funded by private insurance and self-pay and those primarily paid by Medicaid.

Inclusion and Exclusion Criteria

Inclusion Criteria

1. Enrolled client in one of the community treatment settings
2. Over 18 years of age
3. Ability to understand written and spoken English

Exclusion Criteria

1. Any clinical medical/psychiatric condition, severity of that condition, or life situation that in the opinion of the counselors or Drs. [name] or [name] would compromise safe and voluntary study participation (e.g., psychosis, custody conflict).

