Participants will be reimbursed (in a choice of gift cards) \$30 for their time for each baseline, \$20 for post-treatment, and follow-up assessments in increments of \$10 for each 10 questions completed. To minimize attrition, participants will also be offered an addition incentive to be paid at the final 6-month assessment (or end of the 6-month assessment window if they do not complete it). The additional incentive (also in gift cards) will be \$20 for completing 2 of the 3 outcome assessments and \$30 for completing all outcome assessments.

C.7. Data Analytic Plan

Data screening and preliminary analyses. First, exploratory data analysis will be performed to characterize the distributional characteristics of all variables. Frequency distributions and plots will be examined to identify out-of-range values and to assess data distributions. To assess scale reliability and validity, item structure will be examined using Cronbach's alpha and factor analysis. Descriptive statistics, stratified by site and study condition, will be examined to characterize sample characteristics and assess randomization. Baseline characteristics including socio-economic status, gender, suicidality, or substance use found to vary significantly between study conditions will be included as covariates in subsequent outcome analyses. Plots of mean outcomes by assessment point, site, and study condition will be examined to characterize outcome trajectories over time and inform the parameterization of time in the longitudinal models. Because differential attrition can compromise inference about experimental effects, we will compare dropouts and completers on demographic characteristics and available outcome variables.

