Dose Response Analyses. Exploratory analyses will evaluate whether Time (i.e., number of steps) in the intervention phase is associated with improved outcomes in successive steps. The following regression equation depicts the basic dose response model for each outcome: $OUTCOME_{t>0, is} = b_0 + b_1 BL_OUTCOME_{is} + b_2 TAU_TIME_{is} + b_3 PARS_TIME_{is} + u_{0s} + r_{0is} + e_{tis}$, where t indexes the assessment, i indexes the individual, and s indexes the site. In this model, Time will be centered at the beginning of the intervention phase, such that Time = 0 will correspond to the step in which PARS was implemented at a particular site. Time will be coded as a piecewise linear function representing two phases: 1) the TAU phase: the change over time in outcomes during the control period and the 2) PARS phase: a “deflection” term representing the change in slope from the TAU phase following the implementation of PARS. To account for the cluster-randomized design, a random effect for site (u_{0s}) will be included to model the correlation of individuals from the same site. To account for the repeated assessments, a random effect for participant (r_{0is}) will be included to model the correlation of observations within the same individual. The statistical test of the dose-response effect will be the magnitude and statistical significance of the slope of Time during the intervention period.

Power Analysis. We base our power analysis on a stepped wedge design³⁵ evaluating the difference in the rate of help-seeking behavior at month 1 (post-intervention) among those receiving PARS vs. TAU. Based on our pilot study of PARS, we anticipate a 15.6% baseline rate of help seeking behavior, which we expect to increase to 28.1% at post-intervention (1-month) follow-up. Based on the proposed stepped wedge design in which 10 individuals are recruited per site in each of the 6 steps ($N = 900$), we will have 89% power to detect the 12.5% difference in the rate of help-seeking behavior. Assuming 25% fewer participants ($N = 675$, 7.5 individuals per site per step), due to under-recruitment and/or attrition, there will still be 80% power to detect an intervention effect. This represents a conservative estimate of statistical power as the full longitudinal model will leverage data from all participants, including those with incomplete follow-up data.

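### Adjustment covariates are chosen by the significance of baseline imbalance; a list fixed in advance would be sounder, although the primary test hardly depends on it

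*SAP*

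**What the plan says.** The rule stands under data screening and preliminary analyses in SAP section C.7. It takes baseline characteristics, with socio-economic status, gender, suicidality and substance use as examples, and provides that those "found to vary significantly between study conditions will be included as covariates in subsequent outcome analyses". The SAP names no test, no significance level and no allowance for step or site. Its wording leaves the candidate list open beyond the four examples. The same paragraph uses the baseline comparison to judge whether randomization worked.

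No other section fixes a covariate set. The primary model in C.7 has fixed terms for Step, Setting, Treatment, Time and Treatment by Time, with random effects for site and participant. The treatment effect is tested by the interactions b11 to b13.

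On the design, SAP section C3 says that "the 15 sites will be randomly assigned to 5 groups of three sites each". All sites are TAU at Step 1 and all are PARS at Step 6. The power analysis assumes that "10 individuals are recruited per site in each of the 6 steps". Protocol section 5.1 adds that "when we return to the site at each step, we will be recruiting from a different pool of clients".

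**The concern.** Two things are wrong with the rule.

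First, a p-value for imbalance does not measure prognostic value. A strong predictor that happens to balance is left out, and a weak one that happens to differ goes in. The covariate set then changes by chance from one realisation of the trial to the next, for three primary outcomes and for every later analysis that the rule reaches.

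Second, the comparison between conditions does not mean here what it means in an individually randomized trial. Sites are randomized to the timing of the switch, and each step recruits new clients, so PARS clients come later by construction. Correct randomization can still produce differences that an unadjusted test calls significant, because case-mix has drifted or because sites differ.

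At stake are pre-specification and some precision in analyses that compare different clients.

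**Working it through.** **The plan's own figure.** The rule carries no figure. The only design calculation in the SAP is power of 89% at N=900 and 80% at N=675 for month-1 help-seeking. It states no alpha, ICC or variance convention. With a stepped wedge variance formula and an assumed two-sided 5% level, control-rate variance and ICC 0.05 give 89.3% and 80.5%; average variance and ICC 0.005 give 89.1% and 79.9%. The figures can be matched, but they do not fix an ICC for use below.

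**Separation in time** (SAP Figure 1, 15 sites, 10 clients per site and step).
- TAU site-steps at Steps 1 to 5: 15, 12, 9, 6, 3 (45 in all). Mean step = (15 + 24 + 27 + 24 + 15)/45 = 105/45 = 2.33.
- PARS site-steps at Steps 2 to 6: 3, 6, 9, 12, 15 (45 in all). Mean step = (6 + 18 + 36 + 60 + 90)/45 = 210/45 = 4.67.
- The gap is 2.33 steps. The SAP says "there will be six steps. Steps will be 6 months each", which makes it 14 months. The Protocol says "In our Stepped wedge design, each step is 4 months", which makes it 9.3 months.

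**Flag rate from clustering alone.** Take an unadjusted comparison of 450 with 450 at 5%, no drift, total variance 1 and site ICC ρ. A site's weight in the difference of means is (PARS clients minus TAU clients)/450. For Groups 1 to 5 this is +40, +20, 0, -20 and -40 over 450, with three sites each.
- Sum of squared weights = 3 × (1600 + 400 + 0 + 400 + 1600)/450² = 12,000/202,500 = 0.0593.
- True variance = 0.0593ρ + (1 - ρ) × 2/450. The variance the test assumes is 2/450 = 0.00444.
- Ratio = 1 + 12.33ρ. Flag rate = 2Φ(-1.96/√ratio).

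| Site ICC (assumed) | Variance ratio | Flag rate |
|---|---|---|
| 0 | 1.00 | 5.0% |
| 0.01 | 1.12 | 6.4% |
| 0.02 | 1.25 | 7.9% |
| 0.05 | 1.62 | 12.3% |
| 0.10 | 2.23 | 19.0% |

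With four independent candidates, at least one is selected with probability 1 - 0.95⁴ = 18.5% at ICC 0, and 1 - 0.877⁴ = 41% at ICC 0.05.

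**Flag rate from drift.** Take a characteristic with 50% prevalence and no clustering. The standard error is √(2 × 0.25/450) = 3.33 points.
- Drift of 2 points per step: difference 2.33 × 2 = 4.67 points, z = 1.40, flagged 29% of the time.
- Drift of 3 points per step: difference 7.0 points, z = 2.10, flagged 56% of the time.

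In simulation (4,000 trials per setting, ICC 0 to 0.05, drift 0 to 0.10 SD per step), a contrast adjusted for step and site rejected 4.5% to 5.4% of the time throughout. The unadjusted test rejected 5% to 94% of the time.

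**Effect on the primary test.** A baseline covariate is constant within a client. In the change from baseline to month 1, its term cancels, as do the Step terms and the random intercepts. With complete data and a linear model, b11 is the difference between conditions in mean change, so the covariate cannot move it. Simulation agreed:
- Linear, complete data: b11 and its standard error were unchanged by a strong drifting covariate. With dropout that depended on the covariate, the standard error fell by about 0.6%.
- Logistic, 900 clients, four assessments, covariate worth 0.8 logits per SD, 12 datasets per setting, no site term: the mean z for b11 went from 3.034 to 3.031 with complete data, and from 3.54 to 3.55 with 25% of follow-ups missing. The largest single changes were 0.04 and 0.10.

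**Effect on between-client terms.** In the linear check with a strong covariate, the standard error of the between-client PARS term fell from 0.093 to 0.075, a ratio of 0.81. The dose-response model in C.7 also compares clients across steps and has no Step indicators. It already adjusts for the baseline outcome, so the gain there applies only to variance that remains after that.

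**The case against.** The case against giving this weight is strong. Step, site and participant effects are already in the primary model, and the tested interactions are within-person. If drift causes a variable to be flagged, a covariate enters that a fixed list would have contained anyway. The drift and ICC values are assumed, and the SAP names no test, so the unadjusted comparison is itself inferred from the wording. Baseline comparison also has a real use here. Clients are recruited after their site's condition is set and without blinding (Protocol 10.6), so a difference may reflect who agreed to join. An assumed selection effect of 0.2 SD at ICC 0.01 would be flagged 84% of the time unadjusted and 39% adjusted. The SAP expects little of this, "given 98% of those approached in our pilot study consented".

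All of that stands, and it limits the point in two ways.

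A reader might infer that the baseline test mainly detects drift and clustering. The documents do not support this: with no drift and ICC of 0.01 or less, flags are ordinary chance at 5-6%.

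A reader might also infer that the primary test loses power. For a cross-sectional month-1 contrast at ICC 0.02, z is 2.94 (power about 84%). Dividing by √0.9 or √0.8, for covariates explaining 10% or 20% of variance, gives 3.10 or 3.29 (87% or 91%). That arithmetic is right, but it applies a linear formula to a contrast that is not the tested one, with assumed ICC and R².

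The objection does not justify the rule itself. Selecting on chance is no better than selecting on drift, and a check on recruitment does not require that its p-values choose the model.

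**Conclusion.** The rule should go, as a minor and essentially free improvement. Two parts of this rest on the documents alone: covariates are selected by significance of imbalance, and condition is separated from calendar time by 2.33 steps on average. The flag rates rest on assumed drift and ICC, on an unadjusted test at 5%, and on equal enrolment of 10 per site and step.

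The consequence for b11 to b13 is negligible. The benefit is that the models for the three primary outcomes are settled before the data are seen. Precision also improves in between-client analyses such as the dose-response model, by an amount that depends on how prognostic the covariates are. The documents do not show that any of the four named characteristics is prognostic, so the argument is for fixing a list by judgement in advance.

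**What to change.** Replace the rule in C.7 with a fixed list entered in every outcome model whatever the observed balance: baseline suicidality, baseline substance-use severity, gender and socio-economic status. Tie each to the instrument actually collected. The SAP (C.5 Measures) and Protocol 5.13 differ on the suicidality and substance-use measures, and neither describes a socio-economic measure. Settle at the same time whether depression joins the list, since C.5 already describes it as a covariate. Omit a covariate where it is itself the outcome's baseline value, as in the exploratory suicidality and substance-use models. Keep Step and site in the primary models as planned.

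Report baseline characteristics descriptively by step and condition, as a check on differential recruitment, without selection by p-value.

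The cost is SAP wording and about four to six degrees of freedom among 900 participants.
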